3 ASSESSMENT AND MANAGEMENT OF RISK

We acknowledge the ethical concern that the study may result in an increase in symptomatic disease in individuals (and their partners) in the no-screening arm. We justify this possible increased risk by an appraisal of the available evidence which reveals that we have no high-quality evidence that the 3-monthly, 3-site Ng/Ct screening in MSM PrEP cohorts (3x3 screening) is beneficial. We do have evidence that 3x3 screening likely results in harm [6, 16]:

1. **Adverse effects of antibiotics** as noted above[15, 36-39].
2. **Arrested immunity** as noted above [29, 30]. If screening results in 'arrested immunity' it may thus paradoxically increase Ng/Ct prevalence/symptomatic disease.
3. **Certificate of health effect.** A number of studies have argued that screening may result in a "certificate of health" effect whereby those screened may feel that if they come for regular screening this gives them a bill of health that means they can relax safety devices perceived to be onerous such as condom use [16, 40].

Our risk assessment concludes that based on the available evidence stopping screening may be associated with either an increase or a decrease (given arrested immunity) in symptomatic Ng/Ct infections and Ng/Ct spread. Stopping screening will almost certainly be associated with a lower antimicrobial exposure and lower costs.

To minimize the risks, the study is planned to be conducted in a limited and closely-monitored cohort of MSM, already attending scheduled visits at the 5 HIV PrEP clinics. As such, participants will continue to receive appropriate counselling related to practicing safe sex. Participants in the intervention arm will be followed-up with the same intensity and frequency as participants in the comparator arm. In both arms, symptomatic infections, including contact tracing, will be treated throughout the study period and according to standard of care. The safety monitoring board will evaluate if there is an increase in the incidence of symptomatic Ng/Ct infections at the 6 month visits in the non-screening arm. If this would exceed a pre-specified threshold, the study will be stopped (See Section 10).

4 OBJECTIVES AND ENDPOINTS / OUTCOME MEASURES

Study hypothesis

The study hypothesis is that 3x3 screening in MSM PrEP recipients is not associated with a reduction in the incidence of Ng plus Ct infections over 12 months.

Table 1. PICO Table

Population	All MSM participants aged 18 or older, enrolled to receive HIV PrEP at the Institute of Tropical Medicine, Antwerp (ITM), Hôpital Saint-Pierre (HSP), University Hospital of Gent (UZG), Erasmus Hospital (EH) and Liège University Hospital (CHU) who consented to participate in the trial. Participants must report having had sex with another man in the prior 12 months.
Intervention	Participants in the intervention arm will not be screened for Ng/Ct for a period of 12 months, in reference to the routine practice of screening (and treating screening-positive) participants every 3 months (see 'Comparator'). More specifically, participants in the intervention arm will have 3 site (urethra, pharynx and rectum) sampling performed every 3 months but these testing results will only be reported at the end of the 12 month period. Those testing Ng and/or Ct positive at their last visit in the 12 month period will be recalled and offered treatment even in the case of asymptomatic infection (cfr. current routine care). All individuals with symptomatic infections will be treated according to current best practice guidelines, including contact tracing. Participants in the intervention arm will also be treated if contacted via contact tracing.
Comparator	3x3 screening. For a period of 12 months, all participants will be screened for Ng/Ct at three sites (urethra, pharynx and rectum) every three months according to current Belgian guidelines. If they test positive they will be recalled for treatment for Ng/Ct and contact tracing.
Outcome	
Primary outcome:
 
Incidence rate of Ng plus Ct detected at any site whilst individuals are not screened vs. screened
 
Secondary outcomes:
 
 • Cumulative antimicrobial exposure (ceftriaxone/azithromycin/doxycycline) • Incidence of symptomatic Ng plus Ct • Incidence of syphilis • Incidence of HIV • Cost effectiveness of 3x3 screening vs. no screening • Variations in PrEP users' perceptions towards STI screening (only for ITM subjects)

4.1 Primary objective

To assess if not screening MSM on PrEP for Ng/Ct is non-inferior compared to screening in terms of the incidence rate of these infections over a 12-month period.

4.2 Secondary objectives

- 1) To compare the antimicrobial exposure (ceftriaxone/azithromycin/doxycycline) in the screening and non-screening arms
- 2) To assess if not screening MSM on PrEP for Ng/Ct is non-inferior compared to screening in terms of the incidence rate of symptomatic Ng and Ct infections
- 3) To assess the incidence of syphilis
- 4) To assess the incidence of HIV
- 5) To evaluate the economic impact of cessation of Ng/Ct screening in MSM
- 6) To explore PrEP users' perceptions towards STI screening (only for ITM subjects)

4.3 Endpoints

4.3.1 Primary endpoint

Incidence of Ng plus Ct detected at any site whilst individuals are screened vs. not screened.

Numerators: Cumulative number of diagnoses of Ng plus Ct in 12 months in screening/non-screening arms. Each participant can only contribute one diagnosis of Ct and one diagnosis of Ng per (scheduled or unscheduled) visit - regardless of number of sites infected. Thus each participant can contribute up to 2 diagnoses (Ct/Ng) at each (scheduled or unscheduled) visit. The numerator includes laboratory-confirmed diagnoses made between scheduled visits, performed inside or outside of the study.

Denominators: Number of scheduled study visits with available results for the diagnosis of Ng/Ct. The denominator does not include unscheduled visits^a.

The diagnosis of Ng and Ct will be made via nucleic acid amplification testing (NAAT) performed on rectal and pharyngeal swabs and urine.

In the primary analysis, the primary endpoint (as described above) includes all Ng/Ct diagnoses. Hence it is implicitly assumed that every diagnosis is a new infection. It is however possible that an Ng/Ct infection detected at the 3 to 12 month visit in the non-screening arm is simply a non-resolved infection from the prior visit (see Figure 5)^b. This could spuriously increase the measured incidence in the non-screening group. Because

^a The rationale for this definition of the denominator is to, as closely as possible, reflect time at risk of testing Ng/Ct positive. If an individual misses one of their 4 study follow up visits then this reduces their probability of being diagnosed with Ng or Ct by one quarter (assuming no other relevant variables change). Our denominator definition takes this into account by only including study visits where we have results of Ng/Ct testing. Unscheduled visits are not included as these make up a very small proportion of all visits and could be considered to bias the time at risk estimate.

[figure not shown]
^b Given the natural rate of clearance of Ng and Ct from each site, this probability is very low

this risk only applies to the non-screening arm it results in a bias towards exaggerating the effect of screening on incidence. As such if our study finds that non-screening is non-inferior to screening this finding could not be explained by this bias. In a sensitivity analysis, the numerator of the primary endpoint will only include diagnoses if there was a negative test result at the prior visit.

This is further illustrated for gonococcal infections in Figure 5, where over the 12 month follow up there are 4 incident Ng infections in the 4 individuals considered in the no-screening arm. These 4 incident infections are classified according to the study methodology. These 4 infections actually occurred in 2 individuals on 2 contiguous visits meaning it is possible (though very unlikely) that the second of each of these infections represent merely the end stages of the natural elimination of the first infection which still test positive on Ng Nucleic Acid Amplification Test (NAAT).

This would not occur in the screening arm where both these infections would be treated and eliminated at the visit at which they were first detected. The net effect would be a spurious high incidence of Ng in the no-screening arm. Similar considerations would apply to Ct. Because this bias exaggerates the effect of screening, if our study finds that no-screening is non-inferior to screening then this finding could not be explained by this bias.

Figure 5. The non-resolved infections bias

Test of cure: The studies approach to positive Ng/Ct test results at a test of cure visit is outlined in the 'Test of cure visit' section on page 30 (section 8.4).

4.3.2 Secondary endpoints

- 7) Cumulative antimicrobial exposure (ceftriaxone/azithromycin/doxycycline), measured as number of standard doses per 1000 person-years [41]
- 8) Incidence of symptomatic Ng plus Ct
- 9) Incidence of syphilis
- 10) Incidence of HIV
- 11) Economic impact of cessation of 3x3 screening in MSM in Belgium
- 12) Variations in PrEP users' perceptions towards STI screening (only for ITM subjects)

5 TRIAL DESIGN

This study is a multi-centre, controlled, randomized trial of 3x3 Ng/Ct screening (comparator) vs. no screening (intervention). It will be performed in the PrEP cohorts situated at the ITM, HSP, CHU, UZG and EH. All men in follow up at these five centres who report having had sex with another man in the previous year and are enrolled for PrEP follow up will be eligible to participate in the study. After signing informed consent participants will be randomized via a computer-generated schema to either 3x3 screening or no Ng/Ct screening (see section 8.3). In both arms, participants will be followed up in an identical fashion including 3x3 screening. The only difference between the arms will be that in the screening arm, Ng/Ct results will be sent by the STI Laboratory to the study physicians and these participants will be treated and partner contact tracing will be done. The STI Laboratory will only process the samples/report the results from the non-screening arm at the end of the study. In both arms, all individuals with symptoms compatible with Ng or Ct will be tested and treated for these infections according to current best practice guidelines. At the end of the 12-month study period, participants whose most recent tests were positive for Ng or Ct will receive treatment for these.

6 STUDY SETTING

This multi-centre trial will be performed in 5 different sites: Institute of Tropical Medicine, Antwerp (ITM), Hôpital Saint-Pierre (HSP), University Hospital of Gent (UZG), Erasmus Hospital (EH) and Liège University Hospital (CHU). All MSM participants aged 18 or older, enrolled to receive HIV PrEP at these 5 sites and who consented will be eligible to participate in the trial. Participants must report having had sex with another man in the prior 12 months. There are currently 803/816 /290/260/240 MSM enrolled in the ITM/HSP/EH/CHU/UZG PrEP cohorts.

7 ELIGIBILITY CRITERIA

7.1 Inclusion criteria

- Able and willing to provide informed consent
- Men (born as males) and transwomen aged 18 or more*
- Has had sex** with another man in the last 12 months

- Enrolled in Belgian PrEP program at ITM/HSP/EH/CHU/UZG with approval for TDF/FTC (Tenofovir disoproxil fumarate/Emtricitabine) reimbursement from a Belgian Medical Aid
- Willing to comply with the study procedures and to attend the clinic for the 3-monthly visits

7.2 Exclusion criteria

- Enrolment in another interventional trial
- Tests HIV-positive at screening
- Symptoms of proctitis or urethritis

* Cis-women and transmen will not be eligible to participate. This is because of the concern that undetected Ng /Ct infections may cause pelvic inflammatory disease. According to the literature, and our own experience, the numbers of transmen taking PrEP is very low. To the best of our knowledge, we do not have any transmen in follow up at the ITM PrEP cohort. The number of cis-women taking PrEP in our cohorts is also very low.

** Having had sex with another man is defined as having had peno-oral / peno-anal sex with another man in the last 12-month period.

8 TRIAL PROCEDURES

8.1 Recruitment

8.1.1 *Participant identification*

Potentially eligible participants will be identified by the attending PrEP doctors during their routine 3-monthly visits to the study site for their PrEP follow-up. A typical topic of discussion during PrEP consultations is what the PrEP recipients' preference is for STI screening. As part of these discussions the PrEP recipient will be informed about the GonoScreen Study and they will be asked if they wish to participate. It will be made clear to PrEP recipients that they are not under any pressure to participate in the study. In addition, they will be notified that they are free to leave the study at any point without any bearing on their ongoing PrEP care. The PrEP doctors at each of the 5 participating centres will thus be the only individuals who screen for eligible participants. These same PrEP doctors will also be responsible for confirming study eligibility and taking informed consent from the participants.

Posters and leaflets with information about the study will be available in the waiting room of the study site. These documents and materials will be submitted to and approved by the Ethics Committees (ECs) before use.

Participants at the ITM who declined to participate in the GonoScreen study will be asked whether the social science researcher(s) of this study may invite them for a brief qualitative study (see 8.10). Again, it will be made clear that they are not under any pressure and that they may decline at any time. We will explain that this study would be to explore their opinion towards STI screening, to which there is no correct or incorrect answer.

8.1.2 *Screening*

There are slightly different schemas for screening and starting PrEP in the 5 participating centres. What is most important for the study is that by 3 months after starting PrEP all centres follow their patients up every 3 months. In order to standardise the time periods used to compare incidence

we will only enrol participants from the point when they are on PrEP and their next follow up visit at a 3 monthly interval, which is typically at their first or second PrEP visit. Participants who are already taking part in the PrEP program will be also be eligible and can be enrolled.

There are two schemas used for lab testing:

- **Day-of-visit testing.** The tests for Ng/Ct and other laboratory tests are performed on the day of the clinic visit. The participant is typically contacted the following week in the event of an abnormal laboratory test for further treatment/intervention.
- **Week-prior testing.** Here the laboratory tests are performed the week prior to the clinic visit and the results are available to discuss during the clinic visit.

The results of these tests will be used for documentation purposes after the participant has given consent to participate. The test itself is to be considered as a standard of care screening test.

In the event of a positive test for Ng/Ct at this screening visit, they will receive appropriate therapy regardless of which arm they are assigned to.

If an individual has ***symptomatic*** urethritis or proctitis at the time of the study visit they will not be eligible for study enrolment at that visit. They will however be eligible for enrolment at one of their subsequent study visits if their symptoms have resolved by this time point.

Testing positive for syphilis and receiving treatment for syphilis is not an exclusion criteria for participation at the screening or any other visit.

Eligibility for study participation will be confirmed by the study doctors. Study participants will not receive any reimbursement for participation.

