8.4 Blinding

This study will be unblinded.

Study Participants: The participant will not be explicitly informed to which intervention arm they have been randomized. However it will not be possible to completely blind the participants to which arm they are in, since those in the screening arm who test positive will be recalled for treatment of an asymptomatic infection. In addition, participants will be able to see which arm they are in the 3 weeks after enrolment if they login online to obtain their Ng/Ct results (a service that is in the process of becoming available to all PrEP recipients). If they are in the screening arm they will be able to see either a positive or a negative result for Ng/Ct. If they are in the no-screening arm, no test result will be visible. From this they will be able to deduce which arm they are in.

Doctors and study nurses: The attending doctors will not be blinded. Blinding the attending doctors would be very difficult within this study design as a week after each study visit, the doctors will receive the results of the Ng/Ct screening tests, but only for the participants in the 3x3 screening arm. At this point the doctor will be able to deduce which arm the participant is in. As a result, we have decided that the attending doctors will not be blinded to study arm allocation.

Statistician: The study statistician will be blinded until the statistical analysis plan (SAP) is approved.

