8.7 Trial assessments

These assessments will be performed according to standard of care at each participating centre. In certain centres such as HSP the laboratory tests are performed the week before the clinic visit. These laboratory assessments will be considered to be the laboratory results for that particular visit. Participants in the non-screening arm will not be informed of their results at month 3, 6 and 9. They will only be informed about the result of the sample taken at month 0 and month 12.

Screening/enrolment visit (Day 0):

- Eligibility check
- Informed Consent Procedure
- Demographic and question regarding sexual behaviour
- PrEP questionnaire (only at ITM)
- Ask if symptoms compatible with STI
- Physical examination if symptomatic
- STI history last 12 months
- Antibiotic usage last 6 months
- Randomization
- Collection of results of syphilis and HIV testing (performed according to routine practice)
- Sample collection (according to standard practice of the participating sites.):
 - o Urine sample (first-void) (Ng/Ct NAAT)
 - o Pharyngeal swab (Ng/Ct NAAT)
 - o Anorectal swab (Ng/Ct NAAT)

Visit month 3 (can be between one week earlier and 6 weeks later):

- Ask if symptoms compatible with STI
- Physical examination if symptomatic
- STIs diagnosed since last visit (at study site or outside)
- Antibiotic usage
- Question regarding sexual behaviour
- PrEP questionnaire (only at ITM)
- Collection of results of syphilis and HIV testing (performed according to routine practice)

- Sample collection:
 - o Urine sample (first-void) (Ng/Ct NAAT)
 - o Pharyngeal swab (Ng/Ct NAAT)
 - o Anorectal swab (Ng/Ct NAAT)

Visit month 6 (can be between one week early and 6 weeks late):

- Ask if symptoms compatible with STI
- Physical examination if symptomatic
- STIs diagnosed since last visit (at study site or outside)
- Antibiotic usage
- Question regarding sexual behaviour
- PrEP questionnaire (only at ITM)
- Collection of results of syphilis and HIV testing (performed according to routine practice)
- Sample collection:
 - o Urine sample (first-void) (Ng/Ct NAAT)
 - o Pharyngeal swab (Ng/Ct NAAT)
 - o Anorectal swab (Ng/Ct NAAT)

Visit month 9 (can be between one week early and 6 weeks late):

- Ask if symptoms compatible with STI
- Physical examination if symptomatic
- STIs diagnosed since last visit (at study site or outside)
- Antibiotic usage
- Question regarding sexual behaviour
- PrEP questionnaire (only at ITM)

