- Collection of results of syphilis and HIV testing (performed according to routine practice)
- Sample collection:
 - o Urine sample (first-void) (Ng/Ct NAAT)
 - o Pharyngeal swab (Ng/Ct NAAT)
 - o Anorectal swab (Ng/Ct NAAT)

Visit month 12 (can be between one week early and 6 weeks late):

- Ask if symptoms compatible with STI
- Physical examination if symptomatic
- STIs diagnosed since last visit (at study site or outside)
- Antibiotic usage
- Collection of results of syphilis and HIV testing (performed according to routine practice)
- Sample collection:
 - o Urine sample (first-void) (Ng/Ct NAAT)
 - o Pharyngeal swab (Ng/Ct NAAT)
 - o Anorectal swab (Ng/Ct NAAT)
- Question regarding sexual behaviour
- PrEP questionnaire (only at ITM)
- Experience of study participation and preference for screening vs. no screening of Ng/Ct (only at ITM)

Unscheduled visits:

- Visits for treatment of detected STIs:

If any asymptomatic (in screening arm) or symptomatic (in both arms) STI is diagnosed via screening (including Ct, Ng, syphilis, HIV or hepatitis C) at any stage during the study, the current practice of contacting the PrEP recipient (typically by telephone) as soon as the test result is known (typically within 7 days) will be followed. The person will be asked to return to the clinic at their earliest convenience for standard management, including contact tracing. If the week-prior testing schema is used then the participant will be typically treated on the day of the clinic visit. These STIs will be treated according to our current guidelines [3]. Participants in the non-screening arm who come for STI testing at unscheduled study visits for example if they have symptoms of an STI, will be informed of the STI diagnosis according to local best practice guidelines.

Persons with an HIV diagnosis will be offered optimal antiretroviral therapy and further best practice management according to our existing PrEP protocol [5]. They will exit this study after the diagnosis of HIV is made.

As is currently the case for all PrEP recipients, participants of this study will be able to attend the PrEP/STI clinic at any point in between the scheduled visits for any health including mental-health related concerns. Participants will be encouraged to attend the clinic for any symptoms compatible with an STI.

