Interim analyses are planned at two time points: once 50% and 100% of all study recruits have passed their 6 month visit. For the first interim analysis, data is used of the first 507 enrolled participants (i.e. ordered by randomization date) until 6 months follow-up. For the second analysis, data is used of all enrolled participants until 6 months follow-up. The goal of the interim analyses (at both time points) is to estimate the incidence rate ratio of symptomatic Ng plus CT. Estimates will be based on a Poisson regression model (or a negative binomial regression model if there is overdispersion) with number of symptomatic diagnoses as dependent variable, arm and hospital as independent variables and log(number of visits) as offset. This model will provide estimates of the incidence rate in each arm and the incidence rate ratio (no screening versus screening), together with 95% confidence interval. Visits with missing data on the diagnosis of Ng or Ct, will be excluded from the calculation of the incidence rate (excluded both from numerator and denominator).

7. Analysis of main efficacy outcomes: Incidence of Ng plus Ct

In each arm, the incidence of Ng plus Ct will be estimated together with 95% confidence interval. Estimates will be based on a Poisson regression model (or a negative binomial regression model if there is overdispersion) with number of diagnoses as dependent variable, arm and hospital as independent variables, and log(number of visits) as offset. This model will also provide an estimate of the log incidence rate ratio (no screening versus screening), together with 95% confidence interval. The 'no screening' arm is proven to be non-inferior if the upper limit of the 95% confidence interval is lower than $\log(1.25)$.

Visits with missing data on the diagnosis of Ng or Ct, will be excluded from the calculation of the incidence rate (excluded both from numerator and denominator).

In a sensitivity analysis, the numerator of the primary endpoint will only include diagnoses if there was a negative test result at the prior visit.

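### At week-prior centres symptoms can be asked about with the Ng/Ct result known in the screening arm only, so classification as symptomatic may differ by arm

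*Protocol*

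**What the plan says.** Protocol 8.1.2 describes two laboratory schemas. Under day-of-visit testing the sample is taken at the clinic visit and the result follows. For the week-prior schema the protocol states: "Here the laboratory tests are performed the week prior to the clinic visit and the results are available to discuss during the clinic visit". Section 8.7 carries the second schema into the trial: "In certain centres such as HSP the laboratory tests are performed the week before the clinic visit". For treatment of detected infections it adds: "If the week-prior testing schema is used then the participant will be typically treated on the day of the clinic visit".

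Each scheduled visit in 8.7 lists the item "Ask if symptoms compatible with STI". Knowledge of the routine result differs by arm:

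- Section 8.4 leaves doctors unblinded and says that "the doctors will receive the results of the Ng/Ct screening tests, but only for the participants in the 3x3 screening arm".
- Section 8.7 says: "Participants in the non-screening arm will not be informed of their results at month 3, 6 and 9".
- Section 5 says: "The STI Laboratory will only process the samples/report the results from the non-screening arm at the end of the study".

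Symptomatic Ng plus Ct is a secondary endpoint with a non-inferiority margin of 1.25 (SAP 8.2). It is also the quantity given to the DSMB. SAP 6 states: "The goal of the interim analyses (at both time points) is to estimate the incidence rate ratio of symptomatic Ng plus CT". Protocol 10.1.1 proposes that a ratio above two should prompt serious consideration of stopping.

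Neither document defines a symptomatic infection, says whether symptoms are recorded before or after the result is seen, or provides for blinded classification.

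**The concern.** An outcome label that depends on asking and listening should not be assigned with the laboratory result visible in one arm and hidden in the other. A doctor holding a positive result may probe harder, and a participant told of one may recall minor symptoms. At week-prior centres this can happen at the scheduled visit itself, and only in the screening arm.

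At day-of-visit centres the scheduled question comes before the result. Asymptomatic positives in the screening arm are then recalled, and the symptom question is among the optional items at that unscheduled visit.

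At stake are the DSMB's rate ratio and the 1.25 comparison in SAP 8.2. Both interim looks use data to month 6 only, so every scheduled follow-up visit they use (months 3 and 6) is one with withheld no-screening results. Adjusting for hospital does not help, because the difference lies between arms within a hospital.

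**Working it through.** **Where the asymmetry applies**

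- Day 0: no difference, since participants in both arms are told this result.
- Months 3, 6 and 9: present at week-prior centres.
- Month 12: unclear. Section 8.7 says no-screening participants are told this result, while section 5 puts processing or reporting at the end of the study.

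Section 8.4 has doctors receiving results about a week after each visit. That fits day-of-visit centres and conflicts with 8.1.2 and 8.7 for week-prior centres.

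**Inputs from the documents**

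- Diagnoses per visit in the screening arm, from the table in Protocol 11.1: 0.79 × 0.15 + 0.18 × 0.28 + 0.03 × 0.34 = 0.1791. Four visits give 0.716, which reproduces the stated 0.72. I use 0.72/4 = 0.18.
- Share of participants at HSP (w): 816/2,409 = 33.9% from section 6. Section 11.1 gives 739/2,332 = 31.7% for current counts and 886/3,480 = 25.5% for projected counts.
- Symptomatic diagnoses per visit (s): Protocol 10.1.1 cites over 10% per year for symptomatic urethral Ng, so 0.10/4 = 0.025.

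**Assumptions not in the documents**

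- An upper value of s = 0.04.
- A fraction x = 5% to 10% of otherwise asymptomatic screening-arm positives at HSP recorded as symptomatic because the result is known.
- No corresponding change in the no-screening arm, and the same asymmetry at all visits.

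**Illustration 1: relabelling.** With a true ratio of 2.0,

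observed ratio = 2s / [s + w·x·(0.18 − s)]

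For example, s = 0.025, x = 0.10, w = 0.34 gives 0.05/(0.025 + 0.00527) = 1.65.

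| s | x | w = 0.34 | w = 0.255 |
|---|---|---|---|
| 0.025 | 0.05 | 1.81 | 1.85 |
| 0.025 | 0.10 | 1.65 | 1.73 |
| 0.04 | 0.05 | 1.89 | 1.91 |
| 0.04 | 0.10 | 1.79 | 1.84 |

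The overall range is 1.65 to 1.91. Setting w = 1 gives 1.23 to 1.70 within an affected centre.

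**Illustration 2: differential recording.** Let v be the share of symptomatic infections recorded at scheduled visits, and r the chance that symptoms are recorded in the screening arm relative to the no-screening arm. Both are assumed. Then observed ratio = true ratio / F, with F = 1 + w·v·(r − 1).

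- With w = 0.32, v = 0.5 to 1 and r = 1.1 to 2, F runs from 1.02 to 1.32. A true 2.0 reads 1.97 to 1.52, and a true 1.25 reads 1.23 to 0.95.
- With r = 1 there is no bias. With r below 1 it reverses: r = 0.8 and v = 1 give F = 1 − 0.32 × 0.2 = 0.936, and a true 2.0 reads 2.14.

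**Consequence if F exceeds 1** (assuming 0.10 symptomatic infections per person-year in the screening arm)

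- *Second DSMB look.* Take 507 per arm, six months, no dropout and a true ratio of 2.5. Expected counts are 507 × 0.5 × 0.10 × F = 25.4F and 25.35 × 2.5 = 63.4. The Poisson probability that the observed ratio exceeds 2 is 83% at F = 1, and 73%, 62% and 39% at F = 1.08, 1.16 and 1.32.
- *SAP 8.2.* Take 456 per arm, one year and a true ratio of 1.25. The probability of declaring non-inferiority is Φ(ln F/SE − 1.96), with SE² = 1/(45.6F) + 1/57. It rises from 2.5% to 5.9%, 11.8% and 32.4% at the same values of F.

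**The case against.** The strongest objection is about direction. In the no-screening arm, reporting symptoms is a main route to a test result and treatment, so participants and unblinded doctors there have reason to raise symptoms more. A screening-arm positive is treated whether or not symptoms are noted. The bias could therefore run the other way. This stands: the documents give no recording rates.

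Other points also narrow the concern:

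- Symptom status does not rest on the visit question alone. SAP 5.2 collects it at all visits and includes laboratory-confirmed episodes diagnosed elsewhere.
- Recall is not confined to the screening arm. Section 8.7 contacts asymptomatic positives in the screening arm and symptomatic ones in both arms. No-screening participants tested at unscheduled visits are told the diagnosis.
- The sizes are driven by assumptions. The 5% to 10% and the 0.04 have no source. The cited 10% covers urethral Ng only, so a rate for Ng plus Ct at all sites would probably be higher and the relabelling effect smaller.
- The two-fold figure is a proposal, and the DSMB chooses its own threshold and method. That stands, but the DSMB cannot recover symptom status that was already recorded with the result known.

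None of this supplies the missing rule. Classification with the result visible in one arm only is a weakness whichever way it leans.

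**Conclusion.** The asymmetry is in the text, and neither document guards against it. It can affect the symptomatic rate ratio in SAP 6 and 8.2. It does not change how the primary endpoint counts scheduled-visit positives, because that endpoint includes laboratory-confirmed diagnoses whatever the symptoms.

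A reader might infer that symptomatic infection is in fact recorded more readily in the screening arm and that harm from stopping screening is understated. The documents do not support that. It is one plausible direction, and the more troubling one for a safety ratio, but it is an inference. A reader might also take 1.23 to 1.70 as the likely distortion. That is a within-centre figure which neither the DSMB analysis nor SAP 8.2 uses.

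The supportable statement is conditional. If a known positive prompts more recording, and if only HSP (25.5% to 34% of participants) is affected, a true ratio of 2.0 would read about 1.65 to 1.91 under the relabelling assumptions above. The recording model gives a wider span of 1.52 to 1.97. The point merits a change because the remedy is cheap and removes result-driven labelling of scheduled-visit diagnoses in either direction.

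**What to change.** 1. **Protocol 8.7:** state that in both arms symptom status for each scheduled visit is entered in the eCRF, time-stamped, before any Ng/Ct result for that visit is opened or disclosed, and at sampling where feasible.
2. **SAP 5.2, 6 and 8.2:** define a symptomatic infection, and state that this record decides the classification of scheduled-visit diagnoses in the main analysis.
3. **Symptoms first reported after the result is known:** record them with onset date under a separate flag and include them in a sensitivity analysis. They should not be discarded. The protocol's background puts symptom onset typically 2 to 21 days after infection, so some genuine symptoms will start after sampling. A no-screening participant with the same course could attend unscheduled, test positive and count as symptomatic. Dropping such symptoms in the screening arm would create a new asymmetry.
4. **Reporting:** list the week-prior centres and give the symptomatic rate ratio by testing schema.
5. **Protocol 8.4:** reconcile the stated timing of results with 8.1.2 and 8.7.

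The cost is one recording step moved, an eCRF instruction, short SAP text and one sensitivity analysis. The documents do not say who staffs the week-prior sampling contact. Where asking at sampling is not feasible, asking at the start of the visit before the result is opened serves the same purpose. No testing or treatment changes.
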